## 4. INVESTIGATIONAL PLAN

### 4.1. Overall Study Design

[figure not shown]
This is a Phase 2, randomized, double-blind, double-dummy study in subjects with ET who are resistant to or intolerant of HU (according to modified ELN criteria) with a screening platelet count  $\geq 650 \times 10^9/L$  and WBC count  $\geq 11.0 \times 10^9/L$ . Subjects will be randomized in a 1:1 ratio, stratified by JAKV617 mutation status (positive vs negative), platelet count at screening ( $\geq 1000 \times 10^9/L$  or  $< 1000 \times 10^9/L$ ), and prior anagrelide use (yes vs no) to the following 2 treatment groups:

- Group A: ruxolitinib at a dose of 10 mg BID orally and anagrelide-placebo.
- Group B: anagrelide at a dose of 1 mg BID orally and ruxolitinib-placebo.

The study will enroll approximately 120 subjects. Due to block randomization and stratification, the 2 treatment groups may not each contain exactly the targeted number of subjects (n = 60).

Subjects will receive blinded study treatment for 52 weeks. Options for the open-label treatment phase are detailed in Section 4.1.1. All subjects will be followed for safety (eg, reporting of AEs and SAEs) 30 to 37 days after the last dose of blinded study treatment or open-label study treatment. The overall study design is shown in Figure 1.

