#### 4.5. Overall Study Duration

The study begins when the first subject signs the ICF. The blinded treatment phase is complete and study data analysis can occur for the primary endpoint when all subjects have completed Week 52 or discontinued, and all study data through the Week 52 visit have been entered and the data cleaned and verified. The database will be frozen at this time for the initial data analysis to occur.

The study is completed when the last subject has reached Week 156 (approximately 3 years of treatment). Individual subject participation is expected to average 24 to 36 months.

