### 3. STUDY DESIGN

[figure not shown]
Study INCB 18424-272 is a Phase 2, randomized, double-blind, double-dummy study in subjects with ET who are resistant to or intolerant of HU (modified ELN criteria) with a screening platelet count  $\geq 650 \times 10^9/L$  and WBC  $\geq 11.0 \times 10^9/L$ . Approximately 120 subjects will be enrolled and randomized to the following treatment groups:

- Group A: ruxolitinib at a dose of 10 mg twice daily (BID) orally and anagrelide-placebo.
- Group B: anagrelide at a dose of 1 mg BID orally and ruxolitinib-placebo.

Subjects will receive blinded study treatment for 52 weeks. Subjects originally randomized to ruxolitinib with anagrelide placebo (Group A) who are receiving benefit from therapy can 1) continue receiving open-label ruxolitinib until the study is concluded or they meet discontinuation criteria, or 2) choose to discontinue therapy. Subjects originally randomized to receive anagrelide plus ruxolitinib placebo (Group B) have 3 options: 1) they may cross over to begin receiving ruxolitinib if they meet eligibility criteria after consultation with the sponsor and may then continue until the study is concluded or they meet discontinuation criteria; 2) they may continue receiving anagrelide until the study is concluded or they meet discontinuation criteria; or 3) they can choose to discontinue therapy. Note that subjects originally randomized to Group B may cross over to receive ruxolitinib at any time during the open-label part of the study.

All subjects will be followed for safety (eg, reporting of AEs and serious adverse events [SAEs]) 30 to 37 days after last dose of blinded study treatment or open-label ruxolitinib. The overall study design is shown in Figure 1.

Figure 1: Study Design

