### 9.1. General Considerations

The analyses for this section will be provided for the safety population. Summary tables may be replaced with listings when appropriate. For instance, an AE frequency table may be replaced with a listing if it only contains a few unique preferred terms reported on relatively few subjects.

For vital sign and laboratory test values, a primary set of the safety analyses will be based on the safety population, and all safety data will be summarized by visit and by treatment group. Separate analyses will be conducted for crossover subjects, and only the assessments that occurred after the crossover will be summarized.

For safety events, a primary set of the analyses will be based on the safety population, and results will be summarized by treatment group up to the end of the randomization period. The end of the randomization period is defined as the earliest of discontinuation or the individual unblinding date. Separate analyses of safety events will be conducted for all subjects, including those who cross over to ruxolitinib from anagrelide and those who continue on ruxolitinib after unblinding. For crossover subjects, only safety events and assessments that occurred in the crossover period will be counted. For subjects originally taking ruxolitinib, safety events and assessments that occurred in both the randomization and open-label treatment periods will be counted. Results will be shown by treatment group (ruxolitinib and ruxolitinib after crossover).

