## **9.2. Adverse Events**

### **9.2.1. Adverse Event Definitions**

A treatment-emergent adverse event (TEAE) is any AE either reported for the first time or worsening of a pre-existing event after the first dose of study drug. Analysis of AEs (as discussed below) will be limited to TEAEs, but data listings will include all AEs regardless of their timing in relation to study drug administration.

An AE will be attributed to the crossover phase if the onset of the newly emerged or worsened AE is on or after the start date on ruxolitinib. If an end date of the event is after the start date for ruxolitinib, but the onset is registered before the crossover, this event will be attributed to the treatment actually received in the randomized treatment phase.

Adverse events will be tabulated by MedDRA preferred term and system organ class. Severity of AEs will be described and graded using the National Cancer Institute (NCI) CTCAE version 4.03 (NCI 2010). The CTCAE reporting guidelines and grading details are available on the Cancer Therapy Evaluation Program website.

A grading (severity) scale is provided for each AE term. If the toxicity is not included in the CTCAE v4.03 criteria, then it will be rated on a scale of 1 to 5 as follows: 1 = mild, 2 = moderate, 3 = severe, 4 = life-threatening, and 5 = death due to AE. All toxicities will be graded based on the worst level reached, not the level that they may have reached if they had not been treated. When the intensity of an AE changes over time for a reporting period (eg, between visits), then each change in intensity will be reported as an AE until the event resolves.

The subset of AEs considered by the investigator to be related to study drug will be considered to be treatment-related AEs. If the investigator does not specify the relationship of the AE to study drug, then the AE will be considered to be treatment-related. The incidence of AEs and treatment-related AEs will be tabulated. Serious AEs will also be tabulated.

Any missing onset date, causality, or severity must be queried for resolution. Unsolved missing values will be handled according to the following rules:

- An unsolved missing causality will be considered treatment-related.
- An unsolved missing severity will be identified as an unknown severity.

For purposes of analysis, all AEs will be considered TEAEs unless the AE can unequivocally be defined as not treatment-emergent.

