| 3.2.10           | Summary of Treatment-Emergent Serious Adverse Events by MedDRA Preferred Term in Decreasing Order of Frequency in Randomized Phase                        | Safety            | X               | X              |
| 3.2.11           | Summary of Treatment-Related Serious Adverse Events by MedDRA System Organ Class and Preferred Term in Randomized Phase                                   | Safety            | X               |                |
| 3.2.12           | Summary of Treatment-Emergent Adverse Events Leading to Dose Interruption by MedDRA System Organ Class and Preferred Term in Randomized Phase             | Safety            | X               |                |
| 3.2.13           | Summary of Treatment-Emergent Adverse Events Leading to Dose Reduction by MedDRA System Organ Class and Preferred Term in Randomized Phase                | Safety            | X               |                |
| 3.2.14           | Summary of Treatment-Emergent Adverse Events Leading to Discontinuation of Study Drug by MedDRA System Organ Class and Preferred Term in Randomized Phase | Safety            | X               | X              |
| 3.2.15           | Summary of Treatment-Emergent Adverse Events Leading to Withdrawal From the Study by MedDRA System Organ Class and Preferred Term in Randomized Phase     | Safety            | X               |                |
| 3.2.16           | Summary of Treatment-Emergent Non-Serious Adverse Events by MedDRA System Organ Class and Preferred Term in Randomized Phase                              | Safety            | X               |                |
| 3.2.17           | Summary of Treatment-Emergent Adverse Events of Special Interest in Randomized Phase  | Safety            | X               |                |
| 3.2.18           | Overall Summary of Treatment-Emergent Adverse Events in All Ruxolitinib Treated Phase   | Safety            | X               |                |
| 3.2.19           | Summary of Treatment-Emergent Adverse Events by MedDRA System Organ Class and Preferred Term in All Ruxolitinib Treated Phase                             | Safety            | X               |                |
| 3.2.20           | Summary of Treatment-Emergent Adverse Events by MedDRA Preferred Term in Decreasing Order of Frequency in All Ruxolitinib Treated Phase                   | Safety            | X               |                |

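### Adverse events on open-label anagrelide after unblinding fall in no planned adverse event or grade-shift table

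*SAP*

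**What the plan says.** **The option.** Protocol section 4.1.1 and SAP section 3 give Group B three choices after unblinding: cross over to ruxolitinib, stop, or stay on anagrelide, in which case "they may continue receiving anagrelide until the study is concluded or they meet discontinuation criteria". A subject who stays may still cross over later in the open-label part. On duration, Protocol section 4.5 states: "The study is completed when the last subject has reached Week 156".

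**The safety-event sets.** In the primary set, SAP section 9.1 says "results will be summarized by treatment group up to the end of the randomization period", and defines that end as the earlier of discontinuation and individual unblinding. A second set is announced for all subjects, but the only groups described are subjects who cross over to ruxolitinib and subjects who continue on it. Its display is then fixed: "Results will be shown by treatment group (ruxolitinib and ruxolitinib after crossover". SAP section 9.3.2 uses the same two-part structure for CTCAE grade shifts.

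**The table list.** The second half of the adverse event tables in SAP Appendix F opens with Table 3.2.18, "Overall Summary of Treatment-Emergent Adverse Events in All Ruxolitinib Treated Phase", and every table after it up to 3.2.34 has the same scope.

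**Attribution.** For an event that starts before crossover and ends after ruxolitinib has begun, SAP section 9.2.1 says "this event will be attributed to the treatment actually received in the randomized treatment phase".

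**The Protocol's promise.** The safety paragraph of the Protocol synopsis says that vital signs, laboratory tests and adverse events will all be tabulated as well as listed. Protocol section 9.4.2 separates only data collected after crossover and sets no cut at unblinding. SAP section 11.1 declares no change to Protocol-defined analyses.

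**The concern.** SAP Amendment 2 brought the open-label options into the design section, but section 9 has no group for subjects who stay on anagrelide. Their adverse events are on-treatment events that the trial collects, yet they belong to neither set: the first has closed and the second is for ruxolitinib only.

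The result is lopsided reporting. Ruxolitinib would have incidence tables by term, grade, seriousness and outcome for its whole open-label course. Anagrelide would have them only to about Week 56. Safety relative to anagrelide is a secondary objective, and the study rationale cites anagrelide's long-term as well as short-term side effects. A reader of the final report would find no tabulated rates for late anagrelide events, and no tabulated anagrelide exposure against which to read the listings.

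**Working it through.** No planned figure needs reproducing. The check is a comparison of sections, followed by simple arithmetic on size.

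**Step 1: does the exposure exist, and are events collected?** Yes. Protocol Table 3 schedules adverse event review at Week 56 and every 12 weeks for subjects who do not cross over, and at end of treatment and safety follow-up. Protocol section 4.1 follows all subjects until "30 to 37 days after the last dose of blinded study treatment or open-label study treatment".

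**Step 2: which planned tables cover which experience?** From SAP Appendix F:

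| Experience | Adverse event tables | CTCAE shift tables | Exposure table |
|---|---|---|---|
| Both arms, up to discontinuation or unblinding | 3.2.1 to 3.2.17 (17) | 3.3.3, 3.3.7 (2) | 3.1.1 |
| Ruxolitinib: Group A from Day 1, Group B from crossover | 3.2.18 to 3.2.34 (17) | 3.3.4, 3.3.8 (2) | 3.1.2 |
| Anagrelide in Group B from unblinding | none | none | none |

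The totals are 17 + 17 = 34 and 2 + 2 = 4. Numbering in these ranges is continuous and none of these rows is redacted, so redaction does not explain the empty row.

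**Step 3: what happens to a late crossover?** An event that starts and ends between unblinding and a later crossover falls after the first set closes and before the second opens. An event that straddles the crossover is sent by SAP section 9.2.1 to the randomized treatment, whose tables section 9.1 has already closed. The two sections conflict, and the text does not say which governs.

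**Step 4: size.** Unblinding is designated as Week 56.
- Subject on anagrelide to Week 156: (156 − 56)/156 = 100/156 = 64% of treatment weeks are outside these tables.
- Subject with 24 months (about 104 weeks), the lower end of the average participation the Protocol expects: (104 − 56)/104 = 48/104 = 46%.
- The number staying on anagrelide is not given, so the range is 0 to about 60. If 10 subjects stayed to Week 156 (an assumption, for illustration): 10 × 100/52 = 19.2 patient-years untabulated. For scale, 60 subjects each completing 56 weeks contribute 60 × 56/52 = 64.6 patient-years.

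**The case against.** **Other outputs reach past unblinding.** This stands. By-visit laboratory tables (3.3.1, 3.3.5, 3.3.9) and the vital-sign tables for the treatment groups have no stated cut at unblinding. SAP section 6.2 tabulates discontinuation of randomized treatment after unblinding with its primary reason. Listings 2.7.2 to 2.7.7 cover all adverse events, including serious and fatal ones. A reader might infer that late anagrelide harms vanish from the report; they do not. But none of these outputs gives incidence by term, grade or seriousness.

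**A listing may be enough.** SAP section 9.1 allows a listing in place of a sparse table, and section 9.2.3 suggests one when 10 or fewer subjects would appear. This also stands if the group is small. It does not cover a larger group, and the SAP does not invoke the rule for this one.

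**The comparison belongs to the randomized phase.** Protocol section 1.4.2.1 sets Week 52 as the time point for comparative analyses. A reader might infer that the comparative safety objective is undermined; the documents do not support that. Subjects who stay on anagrelide are self-selected and unblinded, and no formal comparison with them is planned.

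**The second set is announced for all subjects.** Read alone, that phrase could include anagrelide. The column statement and the table titles settle it as ruxolitinib only.

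Two further inferences should be resisted. SAP section 3 describes follow-up as "30 to 37 days after last dose of blinded study treatment or open-label ruxolitinib", which might suggest that open-label anagrelide subjects are not followed. Protocol section 4.1 covers both drugs, and so does the main text of Protocol section 4.4; only the last line of 4.4 is narrower. And the Protocol says that anagrelide does not appear to halt marrow fibrosis, which is a lack of effect and not a harm attributed to the drug.

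**Conclusion.** The gap is real but is confined to adverse event, grade-shift and exposure tables. Anagrelide events after unblinding, including those that start and end before a later crossover, are in none of the 34 adverse event tables or 4 shift tables and would be seen only in listings. That departs from the Protocol's plan to tabulate adverse events, and the SAP does not declare the departure. The section 9.1 cut and the section 9.2.1 attribution rule also need reconciling.

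For an individual subject, the share of treatment weeks affected is 46% to 64%, assuming unblinding at Week 56 and continuation to Week 104 or Week 156. The effect on the whole report depends on how many subjects take this option, which the documents do not say. The primary endpoint and the randomized safety comparison are untouched. This is a descriptive reporting gap that should be closed, not a threat to the trial's main conclusions.

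**What to change.** In SAP sections 9.1, 9.2.1 and 9.3.2:
- Define an open-label anagrelide period, from individual unblinding until crossover or, without crossover, until the last anagrelide dose plus safety follow-up.
- Assign events with onset in that period to it, including those that continue after a later crossover. This removes the conflict between 9.1 and 9.2.1.
- Add separate descriptive summaries of adverse events, serious events, fatal events, CTCAE shifts and exposure, with exposure-adjusted rates. State which baseline the shift tables use.
- Do not place these beside the all-ruxolitinib counts, which run from Day 1 for Group A. First-year ruxolitinib events would then be set against subjects who had already tolerated a year of anagrelide.
- State that a listing replaces the tables if few subjects are involved, as the SAP already allows.

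As a clerical correction, align the follow-up wording in SAP section 3 and the last line of Protocol section 4.4 with Protocol section 4.1.

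The cost is SAP wording and some added outputs from data already collected; trial conduct does not change. The drawback is a possibly small, self-selected, unblinded group, so the summaries must be labelled descriptive.

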## **9.2. Adverse Events**

### **9.2.1. Adverse Event Definitions**

A treatment-emergent adverse event (TEAE) is any AE either reported for the first time or worsening of a pre-existing event after the first dose of study drug. Analysis of AEs (as discussed below) will be limited to TEAEs, but data listings will include all AEs regardless of their timing in relation to study drug administration.

An AE will be attributed to the crossover phase if the onset of the newly emerged or worsened AE is on or after the start date on ruxolitinib. If an end date of the event is after the start date for ruxolitinib, but the onset is registered before the crossover, this event will be attributed to the treatment actually received in the randomized treatment phase.

Adverse events will be tabulated by MedDRA preferred term and system organ class. Severity of AEs will be described and graded using the National Cancer Institute (NCI) CTCAE version 4.03 (NCI 2010). The CTCAE reporting guidelines and grading details are available on the Cancer Therapy Evaluation Program website.

A grading (severity) scale is provided for each AE term. If the toxicity is not included in the CTCAE v4.03 criteria, then it will be rated on a scale of 1 to 5 as follows: 1 = mild, 2 = moderate, 3 = severe, 4 = life-threatening, and 5 = death due to AE. All toxicities will be graded based on the worst level reached, not the level that they may have reached if they had not been treated. When the intensity of an AE changes over time for a reporting period (eg, between visits), then each change in intensity will be reported as an AE until the event resolves.

The subset of AEs considered by the investigator to be related to study drug will be considered to be treatment-related AEs. If the investigator does not specify the relationship of the AE to study drug, then the AE will be considered to be treatment-related. The incidence of AEs and treatment-related AEs will be tabulated. Serious AEs will also be tabulated.

Any missing onset date, causality, or severity must be queried for resolution. Unsolved missing values will be handled according to the following rules:

- An unsolved missing causality will be considered treatment-related.
- An unsolved missing severity will be identified as an unknown severity.

For purposes of analysis, all AEs will be considered TEAEs unless the AE can unequivocally be defined as not treatment-emergent.

### **9.2.2. Adverse Events of Special Interest or Adverse Events of Clinical Interest**

[REDACTED]

[REDACTED]

[REDACTED] The naming of SMQs/IMQs and grouping of preferred terms into corresponding SMQs/IMQs will be based on the MedDRA version at the time of analyses.

### 9.2.3. Adverse Event Summaries

An overall summary of AEs by treatment group will include the following:

- Number (%) of subjects reporting any TEAEs
- Number (%) of subjects reporting any SAEs
- Number (%) of subjects reporting any Grade 3 or higher TEAEs
- Number (%) of subjects reporting any treatment-related TEAEs
- Number (%) of subjects with TEAEs leading to temporary dose interruption
- Number (%) of subjects with TEAEs leading to dose reductions
- Number (%) of subjects with TEAEs leading to permanent discontinuation of study drug
- Number (%) of subjects with TEAEs leading to withdrawal from the study
- Number (%) of subjects who had a fatal TEAE

The following summaries will be produced by MedDRA term (if  $\leq 10$  subjects appear in a table, then a listing may be appropriate):

- Summary of TEAEs by system organ class and preferred term
- Summary of TEAEs by preferred term in decreasing order of frequency
- Summary of TEAEs by system organ class, preferred term, and worst CTCAE grade
- Summary of Grade 3 or higher TEAEs by system organ class and preferred term
- Summary of treatment-related AEs by system organ class and preferred term
- Summary of treatment-related AEs by system organ class, preferred term, and worst CTCAE grade
- Summary of TEAEs leading to death by system organ class and preferred term
- Summary of treatment-emergent SAEs by system organ class and preferred term
- Summary of treatment-emergent SAEs by preferred term in decreasing order of frequency
- Summary of treatment-related SAEs by system organ class and preferred term
- Summary of TEAEs leading to dose interruption by system organ class and preferred term
- Summary of TEAEs leading to dose reduction by system organ class and preferred term

- Summary of TEAEs leading to discontinuation of study drug by system organ class and preferred term
- Summary of TEAEs leading to withdrawal from the study by system organ class and preferred term
- Summary of treatment-emergent nonserious AEs by system organ class and preferred term

